9.3.4. Adverse Event of Special Interest

Adverse events of special interest (AESI), including both serious or non-serious events, is 1 of scientific and medical concern specific to the Sponsor's product or program, for which ongoing monitoring and rapid communication by the Investigator to the Sponsor could be appropriate.

For the purpose of this study, severe reductions in platelet count $< 50,000/\text{mm}^3$ accompanied by a major MB event or CRNMB event, or platelet count of $< 25,000/\text{mm}^3$ independent of an MB or CRNMB event are considered as AEs of special interest and is subject to 15-day expediting reporting by the Sponsor to the regulatory agencies.

Investigators should report AEs that met the AESI criteria to the Sponsor immediately, and no more than 24 hours of the Investigator's first knowledge of the event.

9.4. Monitoring and Recording Adverse Events

Any pre-existing conditions or signs and/or symptoms present in a patient prior to the start of the study (i.e., before informed consent) should be recorded as Medical History and not recorded as AEs unless the pre-existing condition worsened. The Investigator should always group signs and symptoms into a single term that constitutes a **single unifying diagnosis** if possible. Before a diagnosis is confirmed, all symptoms should be reported as separate AEs.

9.4.1. Serious Adverse Events

In the interest of patient safety, and in order to fulfill regulatory requirements, all SAEs, and any case of platelet count $< 50,000/\text{mm}^3$ (regardless of their relationship to ISIS 766720) should be reported to the Sponsor or Designee within 24 hrs of the Study Center's first knowledge of the event. The collection of SAEs will begin after the patient signs the ICF and stops at the end of the patient's Follow-up Period which is defined as Early Termination Post-Treatment (ETPT) or Post-Treatment Week 15 (PTWK15) visit. When the Investigator is reporting by telephone, it is important to speak to someone in person vs. leaving a message. The Initial Serious Adverse Event Form should be completed, and a copy should be emailed or faxed to the Sponsor or Designee.

Detailed information should be actively sought and included on follow-up Serious Adverse Event Forms as soon as additional information becomes available. All SAEs will be followed until resolution. SAEs that remain ongoing past the patient's last protocol-specified follow-up visit will be evaluated by the Investigator and Sponsor. If the Investigator and Sponsor agree the patient's condition is unlikely to resolve, the Investigator and Sponsor will determine the follow-up requirement.

9.4.2. Non-Serious Adverse Events

The recording of non-serious AEs will begin after the patient signs the ICF and will stop at the end of the patient's Follow-up Period, which is defined as PTWk15/ETPT visit, or the last visit when patient withdraws consent. The Investigator will monitor each patient closely and record all observed or volunteered AEs on the Adverse Event Case Report Form.

9.4.3. Evaluation of Adverse Events (Serious and Non-Serious)

The Investigator's opinion of the following should be documented on the Adverse Event CRF:

9.4.3.1. Relationship to the Study Drug

The event's relationship to ISIS 766720 is characterized by 1 of the following:

- **Related:** There is clear evidence that the event is related to the use of ISIS 766720, e.g., confirmation by positive re-challenge test
- **Possible:** The event cannot be explained by the patient's medical condition, concomitant therapy, or other causes, and there is a plausible temporal relationship between the event and ISIS 766720 administration
- **Unlikely/Remote:** An event for which an alternative explanation is more likely (e.g., concomitant medications or ongoing medical conditions) or the temporal relationship to ISIS 766720 administration and/or exposure suggests that a causal relationship is unlikely (For reporting purposes, Unlikely/Remote will be grouped together with Not Related)
- **Not Related:** The event can be readily explained by the patient's underlying medical condition, concomitant therapy, or other causes, and therefore, the Investigator believes no relationship exists between the event and ISIS 766720

9.4.3.2. Severity

The severity of AEs and SAEs relating to laboratory tests and AEs at the injection site will be graded based on criteria from the Common Terminology Criteria for Adverse Events (CTCAE) Version 5.0, November 2017 (refer to [Appendix D](#)). Any AE not listed in [Appendix D](#) will be graded as follows:

- **Mild:** The event is easily tolerated by the patient and does not affect the patient's usual daily activities
- **Moderate:** The event causes the patient more discomfort and interrupts the patient's usual daily activities
- **Severe:** The event is incapacitating and causes considerable interference with the patient's usual daily activities

If the event is an SAE, then all applicable seriousness criteria must be indicated (criteria listed in Section [9.3.3](#)).

9.4.3.3. Action Taken with Study Drug

Action taken with ISIS 766720 due to the event is characterized by 1 of the following.

- **None:** No changes were made to ISIS 766720 administration and dose
- **Not Applicable:** SAE/AE was reported during Screening Period prior to ISIS 766720 administration
- **Permanently Discontinued:** ISIS 766720 was discontinued and not restarted
- **Temporarily Interrupted, Re-started – Same Dose:** Dosing and/or dosing frequency was temporarily interrupted/changed or delayed due to the AE and restarted at the same dose
- **Reduced Dose:** Dosing was reduced, temporarily interrupted or delayed due to the AE and restarted at the next lower dose or reduced dosing frequency

9.4.3.4. Treatment Given for Adverse Event

Any treatment (e.g., medications or procedures) given for the AE should be recorded on the Adverse Event Case Report Form. Treatment should also be recorded on the concomitant treatment or ancillary procedures eCRF, as appropriate.

9.4.3.5. Outcome of the Adverse Event

If the event is a non-serious AE, then the event's outcome is characterized by 1 of the following:

- **AE Persists:** Patient terminates from the trial and the AE continues
- **Recovered:** Patient recovered completely from the AE
- **Became Serious:** The event became serious (the date that the event became serious should be recorded as the Resolution Date of that AE and the Onset Date of the corresponding SAE)
- **Change in Severity (if applicable):** AE severity changed

If the event is an SAE, then the event's outcome is characterized by 1 of the following:

- **Ongoing:** SAE continuing
- **Persists (as non-serious AE):** Patient has not fully recovered but the event no longer meets serious criteria and should be captured as an AE on the non-serious AE eCRF (the SAE resolution date should be entered as the date of onset of that AE)
- **Recovered:** Patient recovered completely from the SAE (the date of recovery should be entered as the SAE resolution date)
- **Recovered with Sequelae:** The signs/symptoms of the reported SAE have improved but not completely resolved, and a new baseline for the patient is established since full recovery is not expected
- **Fatal:** Patient died (the date of death should be entered as the SAE resolution date)
- **Unknown:** The outcome of the reported SAE is not available, e.g., patient is lost to follow-up

9.4.3.6. Follow-up of Adverse Event

Investigator Follow-Up

During the Study Period, the Investigator should follow each AE until the event has resolved to baseline grade or better, the event is assessed as stable, the patient is lost to follow-up, or the patient withdraws consent. Every effort should be made to follow all SAEs considered to be related to ISIS 766720 or related to study procedures until a final outcome can be reported.

Resolution of AE (with dates) should be documented on the Adverse Event eCRF and in the patient's medical record to facilitate source data verification.

Investigator should follow-up, or support the Sponsor's effort to follow up with all pregnancies reported during the study from either the study patient or the female partner of male study patient until pregnancy outcome is available.

Sponsor Follow-Up

For SAEs, AESI and pregnancy cases in patients who has completed or terminated study, the Sponsor or a Designee should follow-up by telephone, fax, email, and/or a monitoring visit to obtain additional case details and outcome information (e.g., from hospital discharge summaries, consultant reports, autopsy reports) in order to perform an independent medical assessment of the reported case.

9.5. Procedures for Handling Special Situations

9.5.1. Abnormalities of Laboratory Tests

Clinically significant abnormal laboratory test results may, in the opinion of the Investigator, constitute or be associated with an AE. Examples of these include abnormal laboratory results that are associated with symptoms, or require treatment, e.g., bleeding due to thrombocytopenia, tetany due to hypocalcemia, or cardiac arrhythmias due to hyperkalemia. Whenever possible, the underlying diagnosis should be listed in preference to abnormal laboratory values as AEs.

Clinically significant abnormalities will be monitored by the Investigator until the parameter returns to its baseline value or until agreement is reached between the Investigator and Sponsor Medical Monitor or Designee. Laboratory abnormalities deemed not clinically significant (NCS) by the Investigator should not be reported as AEs. Similarly, laboratory abnormalities reported as AEs by the Investigator should not be deemed NCS on the laboratory sheet.

The Investigator is responsible for reviewing and signing all laboratory reports. The signed clinical laboratory reports will serve as source documents and should include the Investigator's assessment of clinical significance of out of range/abnormal laboratory values.

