8.6.1. Stopping Rules for Liver Chemistry Elevations

In the event of laboratory results meeting the following criteria, **and the event is without an alternative explanation as discussed with the Sponsor Medical Monitor** (or appropriately qualified Designee), dosing of a patient with ISIS 766720 will be stopped permanently; values that are not confirmed due to failure to retest or missing lab values will be presumed confirmed:

1. ALT or AST $> 8 \times$ ULN, which is confirmed
2. ALT or AST $> 5 \times$ ULN, which is confirmed and persists for ≥ 2 weeks
3. ALT or AST $> 3 \times$ ULN or the greater of $2 \times$ baseline value or $3 \times$ ULN if the baseline value was $>$ ULN, which is confirmed **and** total bilirubin $> 2 \times$ ULN or INR > 1.5
4. ALT or AST $> 3 \times$ ULN or the greater of $2 \times$ baseline value or $3 \times$ ULN if the baseline value was $>$ ULN with the new appearance (i.e., onset coincides with the changes in hepatic enzymes) of fatigue, nausea, vomiting, right upper quadrant pain or tenderness, fever, rash, and/or concomitant eosinophilia ($>$ ULN)

8.6.2. Stopping Rules for Renal Function Test Results / Temporary Stopping Rules for Renal Function Test Results

In the event of a persistent elevation that is observed over 2 consecutive weeks, for either of the 2 criteria below, dosing of a patient with ISIS 766720 will be suspended temporarily:

1. Serum creatinine increase that fulfills all of the following: ≥ 0.3 mg/dL (26.5 μ mol/L) **and** $\geq 40\%$ above baseline creatinine values **and** $>$ ULN (refer to definition of baseline in Section 8.6)
2. Proteinuria, UPCR > 750 mg/g for baseline > 200 mg/g, or $4 \times$ baseline for baseline < 200 mg/g that is confirmed by repeated UPCR or by a quantitative total urine protein measurement of > 1.0 g/24 hour

The possible dosing re-initiation or follow-up schedule for any events meeting either of these criteria will be determined by the Investigator **in consultation with** the Sponsor Medical Monitor or Designee.

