8.8. Discontinuation of Study Drug/Treatment

A patient must permanently discontinue study treatment for any of the following:

- The patient becomes pregnant. Report the pregnancy according to instructions in Section [9.4](#)
- The patient withdraws consent
- The patient experiences an AE that necessitates permanent discontinuation of ISIS 766720
- The patient develops laboratory test abnormalities that meet any of the stopping rules listed in Sections [8.6.1](#) to [8.6.3](#)
- The patient meets any of the following Exclusion Criteria (see Section [5.2](#)) after discussion with the Sponsor Medical Monitor (or appropriately qualified Designee)
 - Patient needing pituitary surgery or radiation during Treatment Period
 - Patient with a pituitary tumor that is worsening (e.g., either growing, or at risk of compressing or abutting the optic chiasm or other vital structures) as assessed by pituitary/sellar MRI protocol
 - Treatment with any other acromegaly medications

The reason for discontinuation of ISIS 766720 must be recorded in the electronic Case Report Form (eCRF) and source documentation.

Patients who discontinue ISIS 766720 should complete early termination from treatment visit (ETTX) and then enter the Post-Treatment Period) unless consent is withdrawn. Minimally, every effort should be made to complete the ETTX (see [Appendix A](#), Section [6.1.2](#)).

If the patient declines or is unable to participate in the above, the Investigator should clarify what type of follow-up the patient is agreeable to: in person, by phone/mail, through family/friends, via correspondence/communication with other physicians, and/or from review of the medical records. Wherever possible, these patients should continue to be followed up via the agreed means to collect information on AEs, concomitant medications and survival status. At the very least, the patient's status at the end of the protocol defined study period should be ascertained and documented wherever possible. The agreed means of follow-up will be documented in the patient records and the Sponsor notified.

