9.3. Definitions

9.3.1. Adverse Event

An adverse event (AE) can be any unfavorable and unintended sign (including an abnormal laboratory finding, for example), symptom, or disease temporally associated with the use of medicinal (investigational) product, whether or not the AE is considered related to the medicinal (investigational) product.

An AE can therefore be any of the following:

- Any unfavorable and unintended sign (including an abnormal laboratory finding), symptom, or disease temporally associated with the use of a medicinal product, whether or not considered related to the medicinal product
- Any new disease or exacerbation of an existing disease (a worsening in the character, frequency, or severity of a known condition)
- Recurrence of an intermittent medical condition (e.g., headache) not present at Baseline
- Any deterioration in a laboratory value or other clinical test (e.g., electrocardiogram [ECG], X-ray) that is associated with symptoms or leads to a change in study treatment or concomitant treatment or discontinuation from ISIS 766720

Adverse events that are related to a protocol-mandated intervention, including those that occur prior to assignment of study treatment (e.g., screening invasive procedures such as biopsies).

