3.7.2. Adverse Events

The incidence of adverse events (AEs) will be summarized by Medical Dictionary for Regulatory Activities (MedDRA) Version 22.0 (or higher) preferred term (PT) and system organ class (SOC) for:

- Any treatment emergent adverse events (TEAEs).
- Related TEAEs. Related is defined as “Related”, “Possible”, or missing relationship to Study Drug.
- Any TEAEs by severity. At each severity level of subject summarization, a subject is classified according to the highest severity if the subject reported one or more events. AEs with missing severity will be categorized as “Missing” for this summary.
- Serious TEAEs.
- TEAEs leading to permanent Study Drug discontinued.

Serious and non-serious AEs that lead to study discontinuation or investigational drug discontinuation will be listed separately. Non-TEAE will be included and be noted in the subject AE listing.

To determine the AE as treatment-emergent or not, if there is no “Formlink” link, and the AE (start date/time) occurs after the subject’s first dosing date/time, then the AE is treatment-emergent. Otherwise, if the AE (start date/time) occurs prior to the subject’s first dosing date/time, then the AE is not treatment-emergent.

In addition, if there is a “Formlink” link between two AE records, then we compare them pairwise, and consider two cases, where we compare the AE severity (mild/moderate/severe) and seriousness (Yes/No) between the two records in the pair. We chronologically order the 2 records (by AE start date) and refer to the “first” and “second” AE.

Case 1: The first AE record in the pair occurs before first dosing, and the second AE record occurs after first dosing.

If the AE severity or seriousness of the second record is worse than that of the first record, then only the second AE is deemed as a TEAE. Otherwise, neither record is considered as TEAE.

Case 2: Both AE records in the pair occur after first dosing.

Only the worst AE will be deemed as one TEAE.

All TEAEs identified based on the rules above will be summarized in the event number analysis.

Missing Date for Adverse Events

For AEs, the following imputation rules will be applied to impute missing date under conservative principles.

Missing or partial start dates:

If year, month and day are all missing then assign the date of first administration of Study Drug

- If month and day are missing and year is:

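### Protocol 9.3.1 and 9.5.1 are not reconciled: a laboratory change that triggers a dose hold can count as an AE under one section and go unreported under the other, with renal holds least protected

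*Combined protocol and SAP*

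**What the plan says.** **AE definition (Protocol 9.3.1).** The list opens with "An AE can therefore be any of the following". One item is a deterioration in a laboratory value "that is associated with symptoms or leads to a change in study treatment or concomitant treatment or discontinuation from ISIS 766720". No clinical-significance condition is attached.

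**Laboratory abnormalities (Protocol 9.5.1).** A clinically significant result may, in the investigator's opinion, be or accompany an AE. "Examples of these include abnormal laboratory results that are associated with symptoms, or require treatment"; a dose hold is not among the examples. Then: "Laboratory abnormalities deemed not clinically significant (NCS) by the Investigator should not be reported as AEs". The next sentence adds that a value already reported as an AE should not be marked NCS on the laboratory sheet.

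**Laboratory-driven holds.** Under Protocol 8.6.2, when a creatinine or UPCR criterion persists over 2 consecutive weeks, "dosing of a patient with ISIS 766720 will be suspended temporarily". Protocol 8.6.3 suspends dosing for platelet counts between 50,000 and 75,000/mm³ without major or clinically relevant non-major bleeding.

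**Permanent stops (Protocol 8.8).** One reason listed is "The patient develops laboratory test abnormalities that meet any of the stopping rules", in a bullet of its own next to the one for an AE requiring discontinuation.

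**Displays.** The only TEAE summary in SAP 3.7.2 tied to a drug action is "TEAEs leading to permanent Study Drug discontinued". SAP 3.7.4 tabulates confirmed ALT/AST, bilirubin and platelet categories. SAP 3.2.4 tabulates early treatment discontinuations with the reason.

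**The concern.** Safety and tolerability is a primary objective, and incidence and severity of TEAEs is a safety endpoint. The TEAE summaries in SAP 3.7.2 are built from AE records, so consistent AE capture matters.

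Suppose a confirmed, persistent UPCR rise meets 8.6.2 and dosing is suspended. An investigator working from 9.3.1 records an AE, because the value changed study treatment. An investigator who regards the value itself as clinically unimportant and works from 9.5.1 records none. Both have followed the text. In the second case the study-drug action code for a temporary interruption (Protocol 9.4.3.3) is also lost, because it is an attribute of an AE record.

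At stake is whether the TEAE tables mean the same thing at every site for laboratory parameters that Protocol 8.5 monitors because of observations with this drug and other antisense oligonucleotides.

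**Working it through.** The plan states no figure to reproduce. The check compares the passages and adds one piece of arithmetic.

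**Step 1. Does any passage settle the conflict?**

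| Question | 9.3.1 | 9.5.1 |
|---|---|---|
| What brings a laboratory change in? | Symptoms, or a change in study or concomitant treatment, or discontinuation | Clinical significance in the investigator's opinion |
| What keeps it out? | Nothing stated | An NCS judgement |
| Is a dose hold mentioned? | Yes, as a change in study treatment | No |

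The linking sentence in 9.5.1 runs from AE to laboratory sheet: once an AE is reported, the value should not be called NCS. It does not say that a value meeting a hold rule is clinically significant, and neither does Protocol 8.5 to 8.8. The conflict stays open.

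**Step 2. Could a hold rest on a value that an investigator might plausibly call NCS?**

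Inputs:
- Hold trigger for baseline UPCR below 200 mg/g: 4 × baseline (Protocol 8.6.2).
- Entry limit: exclusion 10a starts at 500 mg/g, so a lower value passes without further testing.
- Baseline UPCR: assumed, since the documents give no distribution.

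The trigger lies below the entry limit when 4 × b < 500, that is, b < 500/4 = 125 mg/g.

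| Assumed baseline (mg/g) | Trigger = 4 × baseline (mg/g) | Below 500? |
|---|---|---|
| 25 | 100 | yes |
| 50 | 200 | yes |
| 100 | 400 | yes |
| 124 | 496 | yes |
| 125 | 500 | no |
| 150 | 600 | no |

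The hold also requires persistence over 2 consecutive weeks and confirmation. Confirmation may be by repeat UPCR or by 24-hour protein above 1.0 g. The illustration applies to the repeat-UPCR route: a 24-hour result above 1.0 g exceeds the 1000 mg/24 hr that exclusion 10a uses as its fallback. It does not carry over to the creatinine criterion, which requires a value above ULN.

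**Step 3. What would still be visible without an AE record?**

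| Event | Visible elsewhere? |
|---|---|
| ALT/AST, bilirubin | Yes: confirmed categories, SAP 3.7.4 |
| Platelets | Yes: confirmed bands, SAP 3.7.4; counts below 50,000/mm³ also reported within 24 hours (Protocol 9.4.1) |
| Permanent stop on a laboratory rule | Yes: disposition by reason, SAP 3.2.4 |
| Creatinine, UPCR | In part: by-visit summaries and listings, but no incidence category |
| The hold itself | Dosing CRF; SAP 3.7.1 as published defines only time on study |

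SAP 3.2.1 keeps unscheduled results out of by-visit tables but allows them into abnormality incidence summaries for AST, ALT, platelets and renal parameters. SAP 3.7.4 never defines the renal one. Extra weekly renal tests under Protocol 8.5.4 that carry the unscheduled label would therefore appear only in listings.

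**The case against.** The strongest reply is that the sections can be read together. A value that changed treatment fits 9.3.1, so it is an AE, so it should not be called NCS. Neither section is absolute: 9.5.1 says should not, and 9.3.1 says an AE can be such a deterioration. On this view the conflict arises only if an investigator marks as NCS a value that suspended dosing, and the 500 mg/g entry limit does not define clinical significance for a sustained fourfold rise within one patient.

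That reading is sensible and may be what was intended, but it is not written down. The linking sentence applies only after an AE has been reported, so it cannot decide whether to report one. What stands is that this is an unresolved ambiguity left to judgement, and that the loss is possible, not certain.

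Two further points stand:
- Not all laboratory-driven changes are automatic. Downward adjustment for liver values (8.5.1.1) is optional and needs consultation, and liver stops (8.6.1) apply only without an alternative explanation. The temporary suspensions prescribed on laboratory results are renal and platelet.
- The SAP plans no TEAE table for interruption or reduction. Complete AE reporting would bring the event into the tables but would still not display the hold. Rewording 9.5.1 alone is therefore not enough.

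**Conclusion.** The concern holds as an inconsistency between Protocol 9.3.1 and 9.5.1 that permits different AE recording of the same laboratory-driven hold. It is most consequential for renal holds, where a trigger can lie below the entry limit (assumed baseline UPCR below 125 mg/g, confirmed by repeat UPCR, persistent over 2 consecutive weeks) and the SAP has no incidence category as a back-up. How often this would occur cannot be estimated from the documents.

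Three stronger readings should be resisted:
- *That liver, platelet and renal signals are all biased downwards.* Liver and platelet categories in SAP 3.7.4 do not depend on AE reporting.
- *That laboratory-rule stops disappear because 8.8 lists them apart from AEs.* The bullets are not stated to be mutually exclusive, the reason must be recorded in the eCRF, and SAP 3.2.4 tabulates it.
- *That each missing record lowers TEAE incidence by 1/12 = 8.3 or 1/15 = 6.7 percentage points.* For overall TEAE incidence this needs a patient with no other TEAE. The denominators are also wrong: 12 is the per-protocol target per group, and 15 assumes about 30 patients split equally over two groups, whereas SAP 3.7 summarises safety by maximum dose received and gives no group sizes.

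The change is worth making because it is nearly free and bears on a primary objective, but no bias of known size has been shown.

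**What to change.** **Protocol 9.5.1** (or, failing an amendment, the CRF completion guideline). Qualify the NCS sentence: such abnormalities are not reported as AEs 'unless they meet Section 9.3.1 (symptoms, or a change in or discontinuation of ISIS 766720, or a change in concomitant treatment)'.

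**SAP 3.7.4.** Add incidence categories for creatinine and UPCR using the criteria already in Protocol 8.5.4 and 8.6.2. This supplies the renal summary that SAP 3.2.1 refers to.

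**SAP listing.** List holds and stops made under a laboratory rule, using the laboratory data, the Dosing CRF and the recorded reason for discontinuation. Keep it separate from the TEAE discontinuation table: that table is organised by MedDRA term, and a stop without an AE record has no term to enter. The listing also covers holds already handled under the present wording.

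**Cost.** One clause in the protocol, one set of categories and one listing in the SAP. TEAE counts may be slightly higher. No dosing, hold or stopping threshold changes.
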